9.3 Inclusion and Exclusion Criteria

The number and percent are to be presented for subjects meeting each Inclusion and Exclusion Criteria. Generally, it is expected that the overall percentage will be 100% for inclusion and exclusion criteria, except when data review indicates that inclusion or exclusion criteria have been violated. Exceptions to 100% will be presented as absolute and relative frequencies both overall and within each treatment group. For any patients included in error a narrative will be provided.

10. DEMOGRAPHICS AND OTHER BASELINE CHARACTERISTICS

Baseline characteristics will be compared descriptively between randomised arms at baseline; no inferential tests will be performed.

10.1 Demographics

Age, gender and ethnicity will be reported. Descriptive data will be presented as appropriate to the data type; mean (SD) for age, absolute and relative frequencies for gender and ethnicity.

10.2 Prior and Concurrent Medications

Absolute and relative frequencies of patients receiving prior and concomitant NSAIDs will be tabulated overall and by treatment group.

10.3 Baseline and Screening Conditions

10.3.1 Baseline Medical History

The following will be summarized as absolute and relative frequencies, by treatment group:

- Family history of autoimmune disease (RA, AS, PsA, IBD)
- Family history of premature cardiovascular disease
- Smoking status (never, current, previous)

10.3.2 Baseline Physical Exam

Baseline physical exam findings will be summarised according to data type (mean (SD) for normally-distributed continuous, median (inter-quartile range) for skewed continuous, absolute and relative frequencies for categorical), by treatment group. The following will be summarized:

- BMI (kg/m²)
- Abnormalities
 - Cardiovascular
 - Respiratory
 - Abdomen
 - Neurological
 - Dermatological
 - Hypertension
 - Diabetes
 - Hypercholesterolaemia

10.3.3 PsA Specific Baseline and Screening History

Baseline PsA-specific findings will be summarised according to data type (mean (SD) for normally-distributed continuous, median (inter-quartile range) for skewed continuous, absolute and relative frequencies for categorical), by treatment group. The following will be summarized:

- Percentage of body surface area affected (%)
- PASI score
- mNAPSI
- CPDAI
- PASDAS
- Leeds enthesitis index
- Imaging scores (see Section 3.3.2 for detailed list of WB-MRI & US variables)
- Patient VAS global disease activity
- DLQI score
- SF-36 physical component score
- SF-36 mental component score

10.4 Measurement of Treatment Compliance

A patient will be considered overall compliant for each study period if he/she is missing no more than 20% of the expected doses and not missing 2 consecutive doses of IMP. Golimumab is administered by the study team and will be fully reported; methotrexate compliance is monitored verbally at each visit.

11. EFFICACY ANALYSES

11.1 Primary Efficacy Variable Analysis

The primary endpoint will be assessed in the Full Analysis Set, with patients assigned to the study arms to which they were originally randomised (intention-to-treat analysis). Full descriptive data will be provided for the PASDAS score at week 24. Unadjusted and adjusted estimates of the treatment effect will be obtained; the unadjusted estimate will be considered supplementary to the primary adjusted estimate. We will present the difference between treatment group means and the 95% confidence interval around the difference. Analysis of covariance by multiple linear regression will be used to compare PASDAS between the two treatment groups at week 24, controlling for the values at baseline, and whether or not the patient had clinical polyarthritis at baseline (stratification factor). In the primary analysis the actual stratification status will be used; in a sensitivity analysis the stratification status used at randomisation (irrespective of actual status) will be used if this differs from the actual status. If visual inspection of model residuals indicate that the data violate the assumptions of linear regression, heteroscedasticity-robust standard errors will be specified.

The analysis of PASDAS at week 24 will include the following test of hypothesis:

$$H_0: \mu_1 = \mu_2$$

The alternative hypothesis is:

$$H_1: \mu_1 \neq \mu_2$$

Where μ_1 and μ_2 represent the covariate-adjusted average in arms 1 and 2 respectively

Acceptance of H_1 in favour of treatment arm 1 (Golimumab + MTX) at two-sided significance $p<0.05$, for the Full Analysis Set, will be considered to be a successful demonstration of efficacy.

11.2 Secondary Efficacy Variable Analysis

Full descriptive data will be provided for all secondary endpoints. Adjusted estimates of effect size will be provided for binary secondary endpoints using multiple binary logistic regression; odds ratios and 95% confidence intervals will be presented. This applies to MDA, PsARC response, ACR 20/50/70, PASI75, US remission, steroid therapy required up to week 12 (Y/N). Continuous interval outcomes will be analysed using multiple linear regression; differences between treatment group means and 95% confidence intervals will be presented. This applies to PASDAS, CPDAI, patient global VAS, SF36 PCS and MCS, US outcomes. Count outcomes will be analysed using an appropriate generalised linear model (see Table 11.2.1); incident rate ratios and 95% confidence intervals will be

presented. If negative binomial regression is used, the mean dispersion parameter will be applied. In the case of missing scores for individual joints, the exposure will be amended to indicate the number of joints/enthuses assessed. This applies to the Leeds enthesitis index, the Leeds dactylitis index, & mNAPSI. Severely skewed outcomes for which an appropriate generalised linear model cannot be identified will be analysed using quantile (median) regression; differences between medians and 95% confidence intervals will be presented. If the median is 0 in both groups then alternative point of comparison will be attempted in the following sequence until model convergence is achieved: 75th percentile, 90th percentile, 95th percentile. This applies to PASI & DLQI. All analyses will control for the stratification factor and baseline values of the outcome where relevant. Two-sided significance at $p<0.05$ will be the criterion applied to all secondary outcomes. If a statistically significant difference is not found for the primary outcome, all secondary outcomes will be considered exploratory.

Table 11.2.1: Models to be used for analysis of secondary outcomes

The appropriateness of these models has been determined following initial blind review of the data. In the event that, once allocation is known, the specified model fails to converge, an alternative model will be used and this deviation from the SAP will be highlighted in the trial report

Outcome(s)	Model
LEI	Negative binomial
LDI	Negative binomial
PASI	Quantile (median) regression
mNAPSI	Negative binomial
DLQI	Quantile (median) regression

If multiple imputation models fail to converge due to the level of attrition and/or complexity of the models relative to the number of patients, mixed modelling will be explored as an alternative. For each outcome, a mixed effects model will be specified which mirrors the planned generalised linear or logistic model specified above. The mixed models will include all observations of each outcome, and the same covariates as specified above, in addition to a categorical variable for time. Random intercepts and random slopes for the time variable will be included. In the primary analysis an interaction between treatment group and time will be specified; for planned subgroup analyses a three-way interaction will be specified between treatment group, time, and oligo/polyarthritis status

or symptom duration at baseline. The covariate-adjusted treatment effect will be estimated at each visit via marginal means.

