#### *Efficacy measures*

- **Clinical measures of disease activity**
  - Disease activity measures:
    - PASDAS at 12, 36 and 52 weeks
    - Enthesitis score at 12, 24, 36 and 52 weeks
    - Dactylitis score at 12, 24, 36 and 52 weeks
    - PASI score (28) at 12, 24, 36 and 52 weeks
    - mNAPSI score (29) at 12, 24, 36 and 52 weeks
    - CPDAI score (30) at 24 and 52 weeks
  - Acceptable state or response:
    - Proportion achieving MDA at 12, 24, 36 and 52 weeks
    - Proportion achieving PsARC response at 8, 12, 24, 36 and 52 weeks
    - Proportions achieving ACR20/50/70 responses at 12, 24, 36 and 52 weeks
    - Proportion achieving at least PASI75 at 12, 24, 36 and 52 weeks in the subset of patients in whom at least 3% of the BSA was affected by psoriasis at baseline
  - Composite index test-retest reliability
    - PASDAS score at screening and at baseline visit.
- **Imaging measures of disease activity**
  - Measures of joint/enthesis pathology
    - Total scores for synovitis/enthesis identified by US at 12, 24 and 36 weeks
  - Acceptable state
    - Proportion achieving US remission at 12, 24 and 36 weeks
- **Patient-reported outcomes**
  - Patient VAS global disease Activity at 24 and 52 weeks
  - DLQI at 24 and 52 weeks (31)
  - SF-36 Mental Component Summary and Physical Component Summary at 24 and 52 weeks (32)

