4. STUDY METHODS

4.1 Overall Study Design and Plan

GOLMEPsA is an investigator initiated, randomised, double-blind, placebo-controlled, two-armed, parallel-group, single-centre imaging-aided study. Patients with the following criteria will be recruited:

[figure not shown]
- Treatment-naïve PsA patients classified according to CASPAR criteria^[12]
- <24 month diagnosis
- At least 3 swollen and 3 tender joints or 2 swollen and 2 tender joints and one tender enthesis.

The trial will start with a four-week screening phase, and informed consent will be obtained at the screening visit. A total of 84 patients will be randomised on a 1:1 basis to receive one of the following:

Treatment Arm 1 (Group A): Immediate golimumab (50 mg SC four weekly) and MTX (starting at 15 mg weekly with rapid escalation up to 25 mg over 4 weeks) combination therapy administered for a total duration of 24 weeks.

Treatment Arm 2 (Group B): MTX monotherapy (starting at 15 mg weekly with rapid escalation up to 25 mg over 4 weeks) plus placebo SC injections four weekly for 24 weeks.

Both treatment arms will receive a “bolus” dose of methylprednisolone (120mg IM or equivalent amount intra-articularly in case of oligoarticular, ≤4 swollen joints, presentation) with the aim to achieve rapid ablation of inflammation at baseline. In addition, both treatment arms will adopt a “treat-to-target” (TT) algorithm (see Schematic Diagram) involving further corticosteroid injections (intra-muscular or intra-articular) if not achieving a PsARC response at weeks 8 and 12 (secondary endpoint). Steroid amount given between both visits will not exceed a maximum amount of 120mg methylprednisolone per patient.

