6. SAMPLE SIZE DETERMINATION

Using in-house unpublished data we estimated the minimum clinically important difference to be 0.7 units on the PASDAS; this is similar to a published value for smallest detectable difference of 0.8 units^[13]. We will aim to detect a difference of at least 1 unit between the treatment arms in this study. The standard deviation of PASDAS in the TICOPA MTX rapid escalation arm^[14,15] at 24 weeks (restricted to patients who remained on methotrexate throughout) was 1.57. Assuming $\delta=1$, $\sigma=1.57$, at $\alpha=0.05$ and $1-\beta=0.8$ this would require 78 patients. Originally the sample size for the trial was adjusted to account for 10% drop-out, requiring a total of 88 (44 per group). However, because recruitment had been slower than anticipated, in part due to the SARS-CoV-2 pandemic, drop-out was reassessed once 76 participants had the opportunity to reach the primary endpoint. Only 4 (5%) had withdrawn from follow-up prior to that point. Therefore, the total required sample size was revised down to 84 (42 per group) i.e. allowing for 5% drop-out.

For the whole-body MRI subset, published rules of thumb for pilot studies indicate that between 12 and 30 patients per group should be included. We will aim to continue recruiting patients into the WBMRI subset until there are at least 30 patients (15 per group) with scans available at both baseline and week 24, at which point WB-MRI will cease to be performed in the remaining patients.

To estimate the ICC between two repeated readings of the PASDAS composite index with a confidence interval of width 0.2, we would need 31 patients assuming the ICC is 0.85. For the patient's global assessment of disease activity VAS, which provides the greatest loading on the PASDAS score, $ICC = 0.87^{[1]}$. This element was added in an amendment and will not be available for all patients; we will aim to obtain data from at least 31 patients.

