11.4 Additional unplanned analysis

After breaking the blind, we made the decision to additionally report PASDAS status and response variables that had been published since the inception of the trial. These were PASDAS very low disease activity, PASDAS moderate or good response, and PASDAS meaningful change value for improvement achieved (Y/N). These will be analysed according to the same methods indicated for the binary response variables i.e. adjusted estimates of effect size will be provided for binary secondary endpoints using multiple binary logistic regression; odds ratios and 95% confidence intervals will be presented. All analyses will control for the stratification factor and baseline values of the outcome where relevant. Two-sided significance at $p<0.05$ will be the criterion applied to indicate potential differences between treatment arms; however, as these comparisons were unplanned they will be considered exploratory.

In addition to these unplanned additional endpoints, unplanned additional descriptive summaries of total USGS and USPD will be presented, to help further illustrate that the lack of substantive change in US GLOESS (combined GS and PD score) was similarly observed for its sub-components.

Unplanned descriptive summaries of alternative definitions of US remission will be presented as the proportions achieving remission were very low, possibly because the criteria for joint remission were very strict.

Unplanned descriptive summaries of tender dactylitis count and 'any' dactylitis count will be presented to give further context to the LDI results, which only counts tender dactylitis.

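### US remission was very rare, but SAP 11.2 analyses it by ordinary logistic regression, which gives no finite treatment odds ratio if an arm has no remissions, and no stated fallback covers that case

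*SAP*

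**What the plan says.** The protocol lists as a secondary endpoint "Proportion achieving US remission at 12, 24 and 36 weeks". Under SAP 8.7, remission requires each of 24 joints and 10 entheses to have a grey-scale score below 2 and no power Doppler signal. SAP 8.2 counts early withdrawals as non-responders on binary outcomes.

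SAP 11.2 analyses binary secondary endpoints "using multiple binary logistic regression; odds ratios and 95% confidence intervals will be presented", and its list includes US remission: "This applies to MDA, PsARC response, ACR 20/50/70, PASI75, US remission, steroid therapy required up to week 12 (Y/N". On covariates it says: "All analyses will control for the stratification factor and baseline values of the outcome where relevant". It names no exact, penalised or other sparse-data method.

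SAP 11.4, added after the blind was broken, says that "the proportions achieving remission were very low, possibly because the criteria for joint remission were very strict". Its response is descriptive summaries under alternative remission definitions; the inferential model stays as it was.

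SAP 11.2 has two fallbacks. The note to Table 11.2.1 says that if "the specified model fails to converge, an alternative model will be used", and that this will be reported as a deviation. The table covers LEI, LDI, PASI, mNAPSI and DLQI. The second fallback replaces multiple imputation by mixed models when the imputation models do not converge, and those mixed models mirror the logistic model already specified.

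**The concern.** Maximum-likelihood logistic regression needs events in both arms to give a finite treatment odds ratio. If one arm has none, the likelihood keeps rising as the log odds ratio moves towards plus or minus infinity. Any number the software prints then reflects its stopping rule, and the Wald interval is meaningless. With a rare endpoint and about 40 patients per arm, an empty arm is a realistic outcome.

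US remission is the only acceptable-state measure among the secondary imaging endpoints, and it supports the secondary objective of superiority on US-detected pathology. As written, its planned result may not exist at one or more of the three visits. The replacement would then be chosen with allocation known and no method named in advance. The SAP anticipated the analogous problem elsewhere: where the median is zero in both groups, quantile regression moves through the 75th, 90th and 95th percentiles in a stated order. Rare binary outcomes have no such sequence.

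**Working it through.** **Inputs.** Arm size is from SAP 6: "the total required sample size was revised down to 84 (42 per group) i.e. allowing for 5% drop-out". Allocation is 1:1 (SAP 4.1). Visits are weeks 12, 24 and 36. The remission rate is not given, so 1% to 10% is assumed.

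**The plan's own figure.** For the primary endpoint, n per arm = 2 × (1.96 + 0.842)² × 1.57² / 1² = 38.7, so 39 per arm and 78 in total. Then 78 / 0.95 = 82.1, which rounds up to 83 and, for equal arms, to 84. This matches the SAP. There is no stated figure for US remission.

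**Chance of an empty arm.** With rate p in an arm of 42, P(no remissions) = (1 − p)^42. With a common rate, P(at least one empty arm) = 1 − [1 − (1 − p)^42]².

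| Assumed common rate | P(given arm empty) | P(at least one arm empty) | of which both empty |
|---|---|---|---|
| 1% | 0.656 | 0.88 | 0.43 |
| 2% | 0.428 | 0.67 | 0.18 |
| 3% | 0.278 | 0.48 | 0.08 |
| 5% | 0.116 | 0.22 | 0.01 |
| 7% | 0.047 | 0.09 | 0.002 |
| 10% | 0.012 | 0.02 | below 0.001 |

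With unequal rates, 5% v 10% gives 1 − (1 − 0.116)(1 − 0.012) = 0.13, and 2% v 5% gives 0.49.

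**By total number of remissions.** With no treatment effect and k remissions among 84 patients, P(all in one arm) = 2 × C(42,k) / C(84,k): 0.49 for k = 2, 0.24 for k = 3 and 0.12 for k = 4.

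**Across visits.** At 5%, the chance that at least one of the three visits is affected lies between 0.22 (fully correlated visits) and 1 − (1 − 0.219)³ = 0.52 (independent visits).

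**What maximum likelihood returns.** For 0/42 v 4/42 adjusted for stratum, the printed odds ratio was 1.6 × 10⁵, 8.5 × 10⁶ and 1.3 × 10⁹ at tolerances of 10⁻⁵, 10⁻⁷ and 10⁻⁹. On the same table, one standard routine reported convergence (log odds ratio 21.3, SE 12,225) and another reported non-convergence. A convergence trigger is therefore not a dependable detector.

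**What a penalised fit returns.** Firth logistic regression, adjusted for stratum (17 of 42 per arm assumed oligoarticular), with Wald intervals:
- 0/42 v 2/42: OR 5.2 (0.29 to 92)
- 0/42 v 3/42: OR 7.5 (0.43 to 133)
- 0/42 v 4/42: OR 9.7 (0.56 to 168)

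These are finite and show how little the data can say.

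**The case against.** The strongest reply is that the endpoint is minor and the repair adds little. US remission is one binary item among many secondary outcomes, all of which become exploratory if the primary comparison is not significant. GLOESS and the enthesitis scores also address imaging response and are unaffected. SAP 11.2 already promises full descriptive data, so counts by arm will be shown, and its where-relevant wording already permits dropping the baseline term. A Firth interval of 0.29 to 92 tells a reader scarcely more than 0/42 v 2/42. A new estimator would also be chosen after the results were known. All of this stands. It limits the importance of the point and requires the change to be labelled, but it does not supply a usable planned analysis.

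Three stronger readings are tempting and are not supported:

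- A reader might infer that the software will silently drop terms and patients, so that no fallback can be triggered and imputed datasets cannot be combined. The SAP names Stata 17.0 but does not say how separation is treated or how much US data is missing. What can be shown is scope: the convergence note sits with a table that has no logistic model. Read more widely, it would still name no alternative.
- A reader might count every form of separation, including an empty stratum. By simulation with 30% to 50% oligoarticular (assumed), that gives 31% to 39% at a 5% rate. An empty stratum alone leaves the treatment odds ratio intact. For example, with oligoarticular 0/25 and polyarticular 4/30 v 2/29, the log odds ratio is ln[(4/26)/(2/27)] = 0.731, SE 0.909, whether or not the 25 patients are kept.
- A reader might extend the point to ACR70 or PASI75. Nothing in the documents says that these were sparse.

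**Conclusion.** The concern holds for US remission. The specified model can leave the planned treatment odds ratio without a finite value, and neither fallback covers this. How likely that is depends on a rate the SAP does not give. The chance is 48% or more per visit at common rates of 3% and below, 22% at 5%, and only 2% at 10%. A reader might infer from SAP 11.4 that an arm was in fact empty. It says only that proportions were very low, so that remains unknown. The figures assume 42 analysed per arm and independent patients. Where both arms are empty, no method yields a useful comparison and the counts are the result. The primary analysis and the sample size are unaffected, so this is a worthwhile correction of limited reach.

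**What to change.** Add to SAP 11.2: when US remission at a given visit has zero or very few events in either arm, the treatment effect will be estimated by Firth penalised-likelihood logistic regression with profile-likelihood intervals (or by exact logistic regression). The model will adjust for the stratification factor and omit the baseline-remission term, and the result will stand beside the counts by arm that are already planned. The sponsor should put a number on very few; zero in either arm is the minimum trigger. Record the change in the revision history as post-unblinding and report the result as exploratory, as version 4.0 does for its other late additions.

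The cost is a short paragraph and a standard command. The drawbacks are some shrinkage of the odds ratio and very wide, conservative intervals: simulated coverage was 97% to 99.8%.

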4.3 Method of Treatment Assignment and Randomization

Patients will be randomised on a 1:1 basis to receive combination therapy of golimumab and methotrexate or methotrexate monotherapy and placebo. Randomly-permuted block sizes will be used; randomisation will be stratified by the number of involved joints at baseline (oligoarticular: ≤ 4 joints involved /polyarticular: >4 joints involved). Informed written consent for entry into the trial must be obtained prior to randomisation, subject to the patient meeting the eligibility criteria. Randomization should take place as soon as possible after consent is obtained and must be performed by an authorized member of the clinical team at the site using the LTHT Pharmacy telephone randomisation service.

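### For PASI and DLQI with a zero median in both arms, the percentile compared is chosen by model convergence, which does not show that it is informative

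*SAP*

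**What the plan says.** SAP section 11.2 assigns quantile (median) regression to severely skewed outcomes for which no suitable generalised linear model is found: "This applies to PASI & DLQI". Table 11.2.1 names median regression for both and says the models were judged suitable at a blind data review.

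The fallback has a trigger and a stopping rule. The trigger is a median of 0 in both groups. In that case an "alternative point of comparison will be attempted in the following sequence until model convergence is achieved: 75th percentile, 90th percentile, 95th percentile".

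The section does not define convergence, does not require the chosen percentile to be non-zero, does not hold one percentile across visits or outcomes, and does not name a standard-error method.

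On status it says: "Two-sided significance at $p<0.05$ will be the criterion applied to all secondary outcomes", and also "If a statistically significant difference is not found for the primary outcome, all secondary outcomes will be considered exploratory". Under SAP section 3.2.2, PASI is compared at 12, 24, 36 and 52 weeks and DLQI at 24 and 52 weeks, so six comparisons fall under the rule.

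**The concern.** A quantile-regression fit is a linear programme. It normally has a solution whether or not the percentile is a useful place to compare the arms. If more than three quarters of each arm score zero, the 75th percentile is zero in both. The fit can still converge, and the reported difference is then 0 whatever happened to the patients with skin disease.

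If the fit does fail, the sequence moves into the tail, where few patients determine the estimate and its standard error.

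The trigger uses the median of each group, so the percentile can be settled only after allocation is known. The six comparisons may end at different percentiles and would then not be comparable.

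DLQI is the quality-of-life measure listed in SAP section 3.2.2, and improved quality of life is a secondary objective. A real benefit could be reported as no difference, or described at a percentile with no clinical rationale.

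**Working it through.** **1. The plan's own figure.** SAP section 6 gives a difference of 1, SD 1.57, two-sided alpha 0.05 and power 80%.
- n per arm = 2 × (1.960 + 0.842)² × 1.57² / 1² = 38.7, so 39 per arm and 78 in total, as stated.
- With 5% drop-out, 39/0.95 = 41.1, so 42 per arm. The SAP agrees: "the total required sample size was revised down to 84 (42 per group) i.e. allowing for 5% drop-out".
- Allocation is equal: "Patients will be randomised on a 1:1 basis".
- Neither document gives a zero rate, SD, effect size or power for PASI or DLQI. Every distribution below is assumed.

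**2. Patients above the cut.** Expected number = n × (1 − τ), with n = 42 per arm.
- 75th: 42 × 0.25 = 10.5
- 90th: 42 × 0.10 = 4.2
- 95th: 42 × 0.05 = 2.1

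**3. Does convergence screen out an uninformative percentile?** Quantile regression was fitted by linear programming on treatment, stratum and baseline score, with 42 per arm and 200 data sets per scenario. A further 15% of patients had a zero baseline and were given a zero outcome. Assumed zero rates of 80% versus 90% therefore mean overall zero shares of 0.15 + 0.85 × 0.80 = 83% and 0.15 + 0.85 × 0.90 = 91.5%. Rates of 55% versus 70% mean about 62% and 74.5%.

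| Percentile | Fits that failed (both scenarios) | Difference exactly 0, 55% vs 70% | Difference exactly 0, 80% vs 90% |
|---|---|---|---|
| Median | 0 of 200 | 179 of 200 | 200 of 200 |
| 75th | 0 of 200 | 56 of 200 | 181 of 200 |
| 90th | 0 of 200 | 63 of 200 | 86 of 200 |
| 95th | 0 of 200 | 62 of 200 | 75 of 200 |

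No fit failed, so under the rule as written every data set that met the trigger would have stopped at the 75th percentile. Stata's own convergence and standard-error failures were not tested.

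**4. Power.** Permutation tests, 42 per arm, zero-inflated log-normal scores, no covariates, 600 replicates, 499 permutations. Null rejection was about 5% for every method.

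| Assumed effect | 75th | 90th | 95th | Rank test |
|---|---|---|---|---|
| Share clear only (zeros 55% vs 80%) | 51% | 34% | 26% | 66% |
| Severity only (score ratio 0.4) | 42% | 48% | 46% | 14% |
| Mixed (zeros 55% vs 70%, ratio 0.5) | 56% | 52% | 48% | 46% |
| Mostly clear (zeros 80% vs 92%, ratio 0.5) | 14% | 37% | 35% | 39% |

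The Monte Carlo standard error near 50% is √(0.5 × 0.5/600) = 2 percentage points. No method is best throughout.

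**5. Standard errors.** Null rejection for quantile regression varied widely between simulations. It was 0.5 to 4.3% in one set using sparsity-based and bootstrap standard errors. It was about 20 to 45% at the 90th and 95th percentiles in a covariate-adjusted set using analytic standard errors. The result depends on the distribution and on a standard-error method that the SAP leaves open. Proportional odds rejected about 5 to 8.5% under the null. The 8.5% comes from 200 replicates, with a 95% Monte Carlo interval of 0.085 ± 1.96 × √(0.085 × 0.915/200), or 4.6% to 12.4%.

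**The case against.** The order of percentiles is fixed in advance and is not driven by p-values. The models were chosen at blind review. Section 11.2 promises full descriptive data for every secondary endpoint. PASI75 is analysed separately by logistic regression in patients with at least 3% of body surface affected. Replacing a pre-specified model after unblinding is itself a post-hoc choice. All of this stands, and it limits the weight of the point and the form of the remedy. It does not answer the defect in the stopping rule, and PASI75 does nothing for DLQI.

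Three stronger readings are tempting, and the documents do not support them.

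- **The result rests on about 2 patients per arm.** That count belongs to the 95th percentile, which is reached only after the 75th and 90th fail to converge. The first fallback has about 10 per arm above the cut. Patients below the cut, including those at zero, also help to fix where the percentile lies.
- **The fallback loses most of the power.** This holds against a rank test when treatment changes only the share of clear patients (26% at the 95th against 66%). It reverses when treatment changes only severity (46% against 14%).
- **The fallback will probably be used.** Zero medians are plausible: CASPAR can be met without current psoriasis (protocol Appendix 3), and PASI is administered only if plaque psoriasis is present (protocol section 8.2.15.2). But no distribution is given, and the trigger needs a zero median in both groups, not one.

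**Conclusion.** The concern holds for the stopping rule. Convergence can leave the comparison at a percentile that is zero in both arms and yield a difference of exactly 0, as in 181 of 200 simulated data sets with 80% versus 90% zeros. If the sequence did move on, about 4 or 2 of 42 patients per arm would lie above the cut and analytic standard errors could not be relied on. The target is settled with allocation known and may change across six comparisons.

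No general loss of power is shown. The simulated figures rest on assumed distributions, and the power figures are unadjusted for covariates. The impact is confined to two secondary outcomes, which are exploratory if the primary is not significant. The primary analysis is untouched.

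**What to change.** Keep the trigger as it is (median 0 in both groups). Replace the percentile sequence with one named analysis for PASI and DLQI at all visits: a proportional-odds model adjusted for baseline value and stratum, reporting a common odds ratio with 95% CI, plus the proportion at zero and the quartiles by arm. Check the proportional-odds assumption and confirm type I error at this sample size with more replicates.

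If score units are preferred, fix one non-zero percentile for all visits from data pooled over the arms without using allocation, and use bootstrap intervals.

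The revision history marks the version 4.0 changes as made after unblinding. Label this change in the same way, or report it as a sensitivity analysis beside the planned result. State which percentile each planned result used and whether that percentile was zero in both arms.

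The cost is SAP wording and one standard model. The drawbacks are an odds ratio instead of a difference in score units, a proportional-odds assumption, and probably low power if treatment changes severity without changing the share clear. The rank test's 14% in that scenario points that way, which is why the proportion at zero and the quartiles belong beside the odds ratio.
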